3.2.1 Open label Stabilization Phase

All enrolled subjects begin treatment at a 2.0 mg/day dose, with the dose titrated to 5.0 mg/day after 2 days. Subsequent dose adjustments in set increments are based on the subject's weight at baseline to achieve optimum control of tics up to the maximum recommended doses based on the US labeling, presented in [Table 3.2.1-1](#).

Weight Group	Dosing Adjustments	Target Doses for Stabilization	Maximum Dose
< 50 kg	5 mg and 10 mg	5 mg and 10 mg	10 mg/day
≥ 50 kg	5 mg, 10 mg, and 20 mg	10 mg and 20 mg	20 mg/day

All enrolled dose titration schedule per weight group is provided in [Table 3.2.1-2](#). Subjects with body weight < 50 kg must remain on a minimum stable dose of 5.0 mg or maximum 10.0 mg for a minimum of 12 weeks. Subjects with body weight ≥ 50 kg must achieve a dose of 10.0 mg no later than Week 4 and remain on a stable dose of 10.0 mg or 20.0 mg for a minimum of 12 weeks. For the remainder of the 12-week period, subjects can remain of 10.0 mg or titrate to 20.0 mg as long as efficacy is stable. In order to be titrated from 10.0 mg to 20.0 mg, subject must remain on a dose of 15.0 mg for 1 week (i.e., at least 4 days) prior to being titrated to 20.0 mg. If a subject is titrated to 20.0 mg and subsequently requires down-titration, their dose is reduced to 10.0 mg. If the dose is up-titrated again, the dose must increase from 10.0 mg to 20.0 mg without a 15.0 mg step. Subjects are allowed 1 down titration (only to the minimum dose to achieve stabilization) and a return to the prior maximum dose during the open-label stabilization phase. Up-titration can only occur at scheduled visits, but down-titration may occur at either scheduled or unscheduled visits. Dose adjustments, and a subsequent return to the higher dose, are not allowed after the Week 8 visit. If a subject experience an AE or tolerability issues after the Week 8 visit that require the dose to be down-titrated, regardless of dose level, they must be discontinued. Subjects who meet the YGTSS TTS criteria for stability and remain on a stable dose of IMP for 12 weeks may be randomized into the double-blind phase of the trial prior to the Week 20/EOP visit.

Body Weight	Day 1 (Baseline)	Week 1	Week 2	Week 4	Week 8^a	Weeks 12 to 20^a
< 50 kg	2.0 mg starting dose, increased to 5.0 mg after 2 days	5.0 mg or increase to 10.0 mg	5.0 mg or increase to 10.0 mg	5.0 mg or increase to 10.0 mg	5.0 mg or increase to 10.0 mg	5.0 mg or 10.0 mg
≥ 50 kg	2.0 mg starting dose, increased to 5.0 mg after 2 days	5.0 mg or increase to 10.0 mg	5.0 mg or increase to 10.0 mg or 20.0 mg (via 15.0 mg step) ^b	10.0 mg or increase to 20.0 mg ^b	10.0 mg or 20.0 mg ^b	10.0 mg or 20.0 mg

^a A one-time down-titration and a return to the previous dose is allowed at or before Week 8. No dose adjustments are permitted after the Week 8 visit.

^b Subjects that will be titrated from 10.0 mg to 20.0 mg must remain on a dose of 15.0 mg for 1 week (i.e., at least 4 days) prior to being titrated to 20.0 mg.

An emergency dose reduction blister card is distributed between trial visits where there is a requested dose titration. The blister card has sufficient tablets for 7 ± 2 days. If the subject is advised to reduce the IMP due to tolerability issues, the subject returns for an in-clinic visit within 1 week after initiating the dose reduction blister card.

3.2.2 Double-blind Randomized Withdrawal Phase

Subjects meeting the stabilization criteria are randomized in a 1:1:1 ratio to the half-dose arm, full-dose arm, or placebo arm based on their stabilized dose in the open-label stabilization phase. Weight-based dosing are determined using the body weight measurement from the open-label stabilization phase baseline. See [Table 3.2.2-1](#) for the dosing schedule.

Weight Group	Stabilized Dose	Double-blind Randomized Withdrawal Phase Doses		
		Full-dose Arm	Half-dose Arm	Placebo Arm
< 50kg	5 mg	5 mg	2 mg	Matching placebo
	10 mg	10 mg	5 mg	Matching placebo
≥ 50 kg	10 mg	10 mg	5 mg	Matching placebo
	20 mg	20 mg	10 mg	Matching placebo

All subjects take 2 tablets once daily. The 20.0 mg/day dose taken as two 10-mg tablets. No dose adjustments will be allowed in the double-blind randomized withdrawal phase.

3.3 Trial Population

3.3.1 Number of Subjects and Description of Population

The trial population includes pediatric subjects, 6 to 17 years of age, meeting the current Diagnostic and Statistical Manual of Mental Disorders, Fifth Edition (DSM-5) diagnostic criteria for TD. It is anticipated that approximately 228 subjects will be enrolled in the open-label stabilization phase from approximately 70 sites worldwide in order to randomize approximately 114 subjects into the double-blind randomized withdrawal phase.

3.3.2 Subject Selection and Numbering

All subjects are given a unique 5-digit subject screening identification number preceded by an S (SXXXXX).

3.4 Trial Visit Window

Trial Week is derived by mapping trial day into corresponding trial week windows as specified in [Table 3.4-1](#). Trial Day is derived as: Trial Day=Date of assessment - Date of IMP dosing in the corresponding phase + 1. If there are multiple observations within the same time interval, only the last observation within that time interval is used for the summary tables. The trial week window mapping rules are applicable to all data that are reported by trial week unless those data are reported by scheduled visit.

Table 3.4-1 Trial Days and Trial Week Windows		
Trial Week	Number of Trial Days in Each Phase	
	Open-label Stabilization Phase	Double-blind Randomized Withdrawal Phase
1	1~10	1~10
2	11~20	11~17
3	N/A	18~24
4	21~34	25~34
6	35~48	35~48
8	49~62	49~62
10	63~76	63~76
12	77~90	77~97
14	91~104	N/A
16	105~118	N/A
18	119~132	N/A
20	133~146	N/A

Note: N/A=not applicable.

4 Sample Size

The planned sample size for the double-blind randomized withdrawal phase is 114 subjects (i.e., 38 subjects per treatment group). Assuming the proportion of randomized subjects experiencing relapse during the double-blind randomized withdrawal phase will be 65% in the placebo group and 34% in each of the 2 aripiprazole dose groups, 114 subjects will provide approximately 80% power to detect a hazard ratio of 0.4 for relapse (either aripiprazole dose group versus placebo) at the alpha level of 0.05 (2-sided). Under the above assumptions, a total of 51 relapse events are expected to be observed during the randomization phase. However, subject enrollment will stop when 51 relapse events have accrued or 114 subjects have been randomized, whichever occurs earlier.

The sample size is estimated to allow 1 Interim Analysis at approximately 70% of events accrual time point. The O'Brien-Fleming boundaries were used for sample size calculation of the interim analysis so that the interim analysis will be conducted when 36 relapse events occur. The 2-sided alpha levels for the IA is 0.016, and the alpha left for the final analysis will be 0.045.

In order to randomize 114 subjects, approximately 228 subjects will need to enter the open-label stabilization phase of the trial, assuming that the stabilization rate is 50%.

5 Statistical Analysis Datasets

5.1 Analysis Datasets

The following analysis datasets are defined for the report of this trial:

- Enrolled Sample: The enrolled sample includes all subjects who entered the open-label stabilization phase.
- Open-label Efficacy Sample: The Open-label Efficacy Sample includes all subjects that are administered at least 1 dose of IMP and have at least 1 assessment of efficacy endpoints during the open-label stabilization phase.
- Open-label Safety Sample: The Open-label Safety Sample includes all subjects that are administered at least 1 dose of IMP during the open-label stabilization phase.
- Randomized Sample: The Randomized Sample included all subjects who are randomized into the double-blind randomized withdrawal phase no matter if he/she takes IMP in randomization phase.
- Intent to treat (ITT) Sample: All subjects who are randomized and receive at least 1 dose of randomized IMP will be included in this dataset and analyzed according to the treatment group they are randomized to. The ITT Sample will serve as the primary efficacy dataset for all efficacy endpoints in the double-blind randomized withdrawal phase.

- Randomized Safety Sample: All subjects who receive at least 1 dose of randomized IMP during the double-blind randomized withdrawal phase will be included and analyzed according to the treatment received.

5.2 Definition of Baseline and Last Visit

Baseline for Open-label Stabilization Phase is defined as the last visit with available data prior to the first dose in Open-label Stabilization Phase. Last visit in Open-label Stabilization Phase is defined as the last visit with available data prior to randomization, or on/before early termination in the Open-label Stabilization Phase.

Baseline for Double-blind Randomized Withdrawal Phase is defined as the last visit of the Open-label Stabilization Phase prior to the first dose of double-blind IMP in Double-blind Randomized Withdrawal Phase. Last visit in Double-blind Randomized Withdrawal Phase is defined as the last visit with available data at the completion or on/before early termination for the randomized subjects.

5.3 Handling of Missing Data

The observed case (OC) dataset consist of the actual observations recorded at each visit and will be used to present summaries per trial week for efficacy endpoints. No missing data will be imputed.

6 Primary and Secondary Endpoints

6.1 Primary Efficacy Endpoint

The primary endpoint variable is time from randomization to relapse during the double-blind randomized withdrawal.

6.2 Secondary Efficacy Endpoints

Secondary efficacy endpoints are not applicable.

6.3 Exploratory Efficacy Endpoints

Exploratory efficacy endpoints during the double-blind randomized withdrawal phase include:

- Change from randomization to last visit in YGTSS TTS score;
- Change from randomization to last visit in Total YGTSS score;
- Change from randomization to last visit in CGI-TS Severity score;
- CGI-TS Improvement score at last visit.

6.4 Safety Endpoints

Safety endpoints include the following:

- Adverse events (AEs)
- Laboratory tests (hematology, serum chemistry glycosylated hemoglobin, and thyroid-stimulating hormone (TSH)], urinalysis, and urine pregnancy tests
- Vital signs
- Electrocardiograms (ECGs)
- Abnormal Involuntary Movement Scale (AIMS)
- Barnes Akathisia Rating Scale (BARS)
- Simpson-Angus Scale (SAS)
- Columbia-Suicide Severity Rating Scale (C-SSRS)
- Body weight
- Body mass index (BMI)
- Waist circumference

7 Summary of Trial Data

The following data will be summarized for enrolled sample and randomized sample if applicable.

7.1 Subject Disposition

Disposition of subjects including screened subjects and/or randomized subjects will be reported by phase and treatment group. Subject enrollment will be summarized by age group (6-12 years old and 13-17 years old), region, country and center. Durations of subjects staying in each phase will be summarized by treatment group. Reasons for discontinuations will be tabulated by phase and treatment group. Subjects who complete the Week 12 visit of the double-blind randomized withdrawal phase are defined as trial completers.

7.2 Demographic and Baseline Characteristics

Demographic characteristics including age, weight, height, BMI, waist circumference, sex, race, ethnicity, region (North American, rest of world), categories for weight (< 50kg, >=50 kg) and age (7-12 years old and 12-17 years old) will be summarized using descriptive statistics (frequency, mean, median, standard deviation, maximum, minimum, and percentage when applicable) and reported by treatment group.

Disease characteristics at baseline and psychiatric history (including efficacy assessments and age of initial diagnosis for TD) will be presented by phase and treatment group. In

calculating age of first diagnosis for TD, if both month and day are missing, June 1 is used. If only day is missing, date of 1 is used. If only month is missing, month June is used.

7.3 Treatment Compliance

For each subject, compliance of IMP will be calculated separately for each phase. compliance for open-label stabilization phase will be calculated from number of days exposed to oral aripiprazole divided by number of days in open-label stabilization phase. Compliance will be derived from the total number of oral tablets taken divided by the expected total number of tablets expectedly taken in double-blind randomized withdrawal phase. The expected number of IMP tablets in double-blind randomized withdrawal phase is 2 tablets per day. Proportion of randomized sample reaching at least 50%, 60%, 70%, 80% and 90% compliance for aripiprazole oral tablets in each phase will be tabulated by treatment group in randomized withdrawal phase. Compliance of IMP will also be summarized for enrolled sample in open-label stabilization phase.

7.4 Prior and Concomitant Medications

Proportion of subjects taking concomitant medications will be tabulated by drug classification using the WHO drug dictionary (WHODRUG Global B3, March 2020 or later) by treatment group for randomized sample prior to start of open-label stabilization phase, during open-label stabilization phase, during/after double-blind randomized withdrawal phase, respectively. The concomitant medications tabulation will be summarized for enrolled sample regarding those periods also.

7.5 Protocol Deviations

Protocol deviations will be summarized by classification of deviations, phase and treatment group in addition to by center. Listing will be provided describing the deviations for each enrolled subject with indication of relevance to COVID-19 outbreak if applicable.

8 Efficacy Analyses

8.1 Primary Efficacy Endpoint

8.1.1 Primary Endpoint Analysis

The primary endpoint is time from randomization to relapse during the double-blind randomized withdrawal phase. Relapse is defined as a loss of $\geq 50\%$ of the improvement experienced during the open-label stabilization phase (i.e., improvement at the last

assessment of YGTSS before randomization) on the YGTSS TTS. Since this trial has terminated early due to withdrawal of postmarketing commitment (PMC), only relapse rate will be provided by treatment group for ITT sample.

8.2 Exploratory Efficacy Endpoints

8.2.1 Exploratory Efficacy Endpoints Analysis

Descriptive statistics for the following efficacy endpoints will be provided by trail week and last visit for open-label efficacy sample in open-label stabilization phase and ITT sample in double-blinded randomized withdrawal phase, respectively.

- Change from randomization to last visit in YGTSS TTS score;
- Change from randomization to last visit in Total YGTSS score;
- Change from randomization to last visit in CGI-TS Severity score;
- CGI-TS Improvement score at last visit.

The YGTSS is a semi-structured clinical interview designed to measure current tic severity. This scale consists of a tic inventory, with 5 separate rating scales to rate the severity of symptoms, and an impairment ranking. Ratings are made along 5 different dimensions on a scale of 0 to 5 for motor and vocal tics, each including number, frequency, intensity, complexity, and interference. Summation of these scores (i.e., 0-50) provides a YGTSS-TTS score. The YGTSS ranking of impairment with a maximum of 50 points, is based on the impact of the tic disorder on areas of self-esteem, family life, social acceptance, and school scores. Total YGTSS score is sum of YGTSS-TTS score and impairment score with range of 0 to 100.

The severity of illness and efficacy of IMP for each subject will be rated using the CGI-TS scale. Response choices include: 0 = not assessed; 1 = normal, not at all ill; 2 = borderline mentally ill; 3 = mildly ill; 4 = moderately ill; 5 = markedly ill; 6 = severely ill; and 7 = among the most extremely ill patients. The rater or investigator will rate the subject's total improvement whether it is due to drug treatment. All responses will be compared to the subject's condition at baseline. Response choices include: 0 = not assessed, 1 = very much improved, 2 = much improved, 3 = minimally improved, 4 = no change, 5 = minimally worse, 6 = much worse, and 7 = very much worse.

9 Safety Analyses

Safety analysis will be conducted based on open-label and randomized safety samples, which are defined in [Section 5.1](#). Safety variables to be analyzed include AEs, clinical laboratory tests, physical examinations, vital signs, ECGs, suicidality via the C-SSRS (children's version). In general, safety data will be summarized using descriptive

statistics (where applicable) by treatment group for open-label safety sample in open-label stabilization phase and randomized safety sample in double-blinded randomized withdrawal phase, respectively.

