7.4.3.2 Double-blind Randomized Withdrawal Phase

Exploratory efficacy endpoints during the double-blind randomized withdrawal phase include:

- Mean change from randomization to last visit (Week 12 for completers and withdrawal visit for discontinued subject) in YGTSS TTS score
- Mean change from randomization to last visit (Week 12 for completers and withdrawal visit for discontinued subject) in Total YGTSS score
- Mean change from randomization to last visit (Week 12 for completers and withdrawal visit for discontinued subject) in CGI-TS Severity score
- CGI-TS Improvement score at last visit (Week 12 for completers and withdrawal visit for discontinued subject)

For the above endpoints except the CGI-TS Improvement score, randomization baseline is defined as the assessment taken at the last visit of the open-label stabilization phase prior to the first dose of the randomized IMP.

Variables in the form of change from randomization baseline will be analyzed using mixed model repeated measures (MMRM) under the assumption of missing at random (MAR). The time variable is scheduled visits, which will be treated as a categorical repeated factor. The MMRM model will include terms of treatment, visit, and treatment by visit interactions as fixed categorical effects, baseline as well as baseline by visit interactions as covariates, and a single unstructured covariance matrix assumed for all treatment arms in the model. Restricted maximum likelihood estimates of the treatment difference, their 2-sided 95% CIs and p-values (using Kenward-Roger degrees of freedom) from the MMRM inference will be provided.

The change from randomization baseline to Week 12 of the double-blind randomized withdrawal phase in the above variables will also be analyzed using analysis of covariance (ANCOVA) with missing data being imputed by last observation carried

Protocol 31-14-204

forward. The ANCOVA model will include treatment as a factor and baseline value as a covariate.

To evaluate the sensitivity of the results to missing data that are potentially missing not at random (MNAR), sensitivity analyses will be conducted with multiple imputations for missing data under the assumption of MNAR, which will be detailed in the SAP.

CGI-TS Improvement score from postbaseline visits will be analyzed in a similar fashion to those change from baseline variables except that there will not be adjustment for baseline value in the analyses of CGI-TS Improvement score.

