9.6.2 Suicidality

The incidence of suicidality, suicidal behavior and suicidal ideation will be calculated from the potential suicide events recorded on the C-SSRS (children's version) in the single-blind stabilization phase and double-blind randomized withdrawal phase for the safety samples. Suicidality will be assessed based on C-SSRS data. Data for the Baseline Version of the C-SSRS and Since Last Visit Version of the C-SSRS data will be summarized descriptively and presented in a listing.

The baseline version of C-SSRS is administered at the screening visit and the "Since Last Visit" version is administered at all subsequent visits. Baseline and post-baseline C-SSRS data will be summarized to report the incidence of suicidality, suicidal behavior and suicidal ideation. Suicidality is defined as reporting at least 1 occurrence of any suicidal behavior or suicidal ideation. Suicidal behavior is defined as reporting any type of suicidal behaviors. Suicidal ideation is defined as reporting any type of suicidal ideation.

In addition, C-SSRS data collected post-baseline will also be summarized to report the incidence of completed suicide, emergence of suicidal ideation, emergence of serious suicidal ideation, worsening of suicidal ideation and emergence of suicidal behavior. Any completed suicide is considered as complete suicidality. Emergence of suicidal ideation is defined as having no suicidal ideation at screening and baseline and reporting any type of ideation during treatment. Emergence of serious suicidal ideation is defined as having no suicidal ideation at screening and baseline and reporting any type of suicidal ideation with ideation severity rating of 4 or 5 during treatment. Worsening of suicidal ideation is defined as occurring when the most severe suicidal ideation rating during treatment is more severe than its worst rating at screening and baseline. Emergence of suicidal behavior is defined as having no suicidal behavior at screening and baseline and reporting any type of suicidal behavior during treatment.

10 Pharmacokinetic Analyses

None.

11 Pharmacodynamic Analyses

None.

12 Pharmacogenomic Analyses.

None.

13 Interim Analysis

None.

14 Changes in the Planned Analyses

This trial was terminated due to withdrawal of postmarketing commitment, so the interim analysis specified in the protocol was not to be conducted. The descriptive statistics will be provided for all the efficacy endpoints.

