Appendix 4 Proposed Summary Tables and Data Listings

Proposed Summary Tables:

- CT-1.1.1 Subject Disposition by Phase
- CT-1.1.2 Subject Disposition in Double-Blind Randomized Withdrawal Phase (Randomized Sample)
- CT-1.2.1 Subject Enrollment by Region, Country and Center
- CT-1.2.1 Subject Enrollment by Region, Country and Center (Randomized Sample)
- CT-1.3.1 Subject Enrollment by Age Group at Enrollment
- CT-1.3.2 Subject Enrollment by Age Group at Enrollment (Randomized Sample)
- CT-2.1 Reasons for Discontinuation by Phase (Enrolled Sample)
- CT-2.2 Reasons for Discontinuation (Randomized Sample)
- CT-3.1.1 Demographic Characteristics (Enrolled Sample)
- CT-3.1.2 Demographic Characteristics (Randomized Sample)
- CT-3.2.1 Baseline Disease Characteristics (Enrolled Sample)
- CT-3.2.2 Baseline Disease Characteristics (Randomized Sample)
- CT-4.1 Concomitant Medications: Medications Taken by Phase (Open-Label Safety Sample)
- CT-4.2.1 Concomitant Medications: Medications Taken Prior to Start of Study Therapy (Randomized Safety Sample)
- CT-4.2.2 Concomitant Medications: Medications Taken During Open-Label Stabilization Phase (Randomized Safety Sample)
- CT-4.2.3 Concomitant Medications: Medications Taken During Double-Blind Randomized Withdrawal Phase (Randomized Safety Sample)
- CT-4.2.4 Concomitant Medications: Medications Taken Post Study Therapy Period (Randomized Safety Sample)
- CT-5.1 Descriptive statistics for Relapse Rate (ITT Sample)
- CT-5.2.1 Yale Global Tic Severity Scale - Total Tic Score (YGTSS - TTS) - Mean Change from Baseline by Week - OC (Open-Label Efficacy Sample)
- CT-5.2.2 Yale Global Tic Severity Scale - Total Tic Score (YGTSS - TTS) - Mean Change from Baseline by Week - OC (ITT Sample)
- CT-5.3.1 Total Yale Global Tic Severity Scale Score - Mean Change from Baseline by Week - OC (Open-Label Efficacy Sample)
- CT-5.3.2 Total Yale Global Tic Severity Scale Score - Mean Change from Baseline by Week - OC (ITT Sample)
- CT-5.4.1 Clinical Global Impressions Scale for Tourette's Syndrome (CGI-TS) Severity score - Mean Change from Baseline by Week - OC (Open-Label Efficacy Sample)
- CT-5.4.2 Clinical Global Impressions Scale for Tourette's Syndrome (CGI-TS) Severity score - Mean Change from Baseline by Week - OC (ITT Sample)
- CT-5.5.1 Clinical Global Impressions Scale for Tourette's Syndrome (CGI-TS) Improvement Score - Mean by Week - OC (Open-Label Efficacy Sample)

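### For the exploratory change scores, the SAP replaces the protocol's baseline-adjusted differences from placebo, with 95% CIs, by observed-case descriptive statistics and does not name the analyses it drops

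*SAP*

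**What the plan says.** **Protocol 7.4.3.2.** Change from randomization in YGTSS TTS, Total YGTSS and CGI-TS Severity is analysed by MMRM with baseline and baseline-by-visit covariates. The output is treatment differences with two-sided 95% CIs and p-values. A second analysis of change to Week 12 uses last observation carried forward: "The ANCOVA model will include treatment as a factor and baseline value as a covariate". Multiple-imputation sensitivity analyses under missing not at random are also promised. CGI-TS Improvement is handled similarly but without baseline adjustment.

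**SAP.** Section 8.2.1: "Descriptive statistics for the following efficacy endpoints will be provided by trail week and last visit". Tables CT-5.2.2, CT-5.3.2 and CT-5.4.2 in Appendix 4 share the title ending "Mean Change from Baseline by Week - OC (ITT Sample". Section 5.3 adds, for the weekly efficacy summaries: "No missing data will be imputed". For the primary endpoint, Section 8.1.1 says that "only relapse rate will be provided by treatment group for ITT sample".

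Section 14 gives the reason, "This trial was terminated due to withdrawal of postmarketing commitment, so the interim analysis specified in the protocol was not to be conducted", and then the consequence: "The descriptive statistics will be provided for all the efficacy endpoints".

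**The concern.** No SAP efficacy section or listed efficacy table contains a contrast between arms, a confidence interval or a covariate for these three scores. The protocol had specified all three.

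Withdrawal of a postmarketing commitment is a good reason to give up an interim look and confirmatory testing. It leaves randomization intact and does not stop anyone estimating a difference with an interval. Section 14 names only the interim analysis as not done, so a reader of the SAP alone would not learn that a model-based estimate had been planned.

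Two things are at stake. The tic-severity data from the randomized phase would be reported without an estimate of the effect of continuing aripiprazole. The weekly tables that remain can also mislead, because subjects who relapse are to be discontinued (Protocol 3.1, SAP 3.1.3) and later weeks therefore compare differently selected survivors.

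**Working it through.** **1. Is there a plan figure to reproduce?** Not for these endpoints: the documents give no SD, power or target difference for them. The sizing figures belong to time to relapse (Protocol 7.1) and reproduce. The hazard ratio is ln(0.66)/ln(0.35) = 0.396 against the stated 0.4. Events are 38 × 0.65 + 2 × 38 × 0.34 = 50.5 against 51. They do not bear on this point except through the relapse rates used in step 3.

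**2. What can a reader recover from the SAP tables?** SAP 7.2, for demographics, lists "descriptive statistics (frequency, mean, median, standard deviation, maximum, minimum, and percentage when applicable". If the same set is used in 8.2.1, and if the tables are split by arm, a reader can compute a raw difference in mean change and an interval from the means, SDs and counts. Section 8.2.1 does not actually say the tables are by treatment group; that is inferred from the ITT tables and Section 8.1.1. The adjustment for the randomization score cannot be recovered.

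**3. Whom do the late weekly means describe?** Under the planning rates, and ignoring other dropout, the relapse-free subjects at the end are:
- placebo: 38 × (1 − 0.65) = 13.3, about 13 of 38;
- each aripiprazole arm: 38 × (1 − 0.34) = 25.1, about 25 of 38.

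The Week 12 observed-case mean rests on these subjects plus any whose relapse is first recorded at that visit. Placebo loses more of its worst outcomes, which would tend to shrink the visible difference. The last-visit value defined in SAP 5.2 keeps the relapsers' final scores.

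**4. How wide would the interval be?** For one arm against placebo with n per arm, the half-width in SDs of the analysed outcome is t(0.975) × √(2/n) × √(1 − r²). Here r is the correlation of that outcome with the randomization score, and the degrees of freedom are 2n − 2, or 2n − 3 with the covariate. The number randomized and r are not in the documents, so both are assumed:

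| n per arm | r = 0 | r = 0.7 |
|---|---|---|
| 5 | 1.46 | 1.07 |
| 10 | 0.94 | 0.67 |
| 20 | 0.64 | 0.46 |
| 38 (full plan) | 0.46 | 0.33 |

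**5. What does adjustment gain over raw change?** Let ρ be the correlation between randomization and last-visit scores.
- Equal variances at the two times: the SE ratio, ANCOVA to raw change, is √((1 + ρ)/2) = 0.806, 0.866 and 0.922 at ρ = 0.3, 0.5 and 0.7. The SE is 19%, 13% and 8% smaller.
- Last-visit SD 1.5 times the randomization SD (assumed): the ratio is √[2.25(1 − ρ²)/(3.25 − 3ρ)] = 0.933, 0.982 and 0.999. The gain is about 7%, 2% and 0%.

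Unequal variances are plausible here. Randomization scores are restricted by the response rule, while last-visit scores mix relapsers and non-relapsers.

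**6. Can the model be fitted?** A three-arm ANCOVA has four mean parameters. An unstructured MMRM over eight visits has 8 × 9/2 = 36 covariance parameters and may not be estimable in a small sample.

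**The case against.** The best defence is that this is a disclosed reduction of exploratory analyses in a trial that stopped early. Much of that stands, and it rules out several stronger readings.

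- A reader might infer that the change is hidden. It is not: Section 14 states it, and Section 8.1.1 ties the reduced primary analysis to the termination. What is missing is a list of the dropped analyses.
- A reader might infer that no measure of uncertainty remains. Arm SDs would permit a crude unadjusted interval. What is lost is a reported interval for the difference, and the adjustment.
- A reader might infer that the primary objective goes unserved on account of these scores. Protocol 7.4.1 ties that objective to time to relapse. The change scores are exploratory, with no error control or power statement.
- A reader might infer that a chance imbalance in randomization score passes in full into the raw change. It enters only through (1 − slope). At an assumed 10 per arm, the imbalance has SD √(2/10) = 0.45 randomization SDs. With equal variances (slope = ρ), its effect on change has SD 0.31, 0.22 and 0.13 at ρ = 0.3, 0.5 and 0.7.
- The last-visit value resembles last observation carried forward, the protocol's secondary method. After a sponsor termination it mixes relapse exits, completers and truncated follow-up. This is a real limit on interpretation and has to be stated with the result.

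The defence does not show that administrative termination prevents estimation. Nor does it show that observed-case weekly means are a better summary than a last-visit contrast.

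**Conclusion.** The point holds at minor severity. For the three change scores, the SAP drops a protocol-specified, baseline-adjusted difference with a 95% CI and does not name the analyses dropped. The reason given does not require this.

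The practical loss depends on how many subjects were randomized, which the documents do not say. The interval would be informative near the full plan (half-width 0.33 to 0.46 SD) and wide at 5 to 10 per arm. The precision gain of 8% to 19% from adjustment requires equal variances at randomization and last visit, and may be close to nil otherwise. The firmer reasons for the change are a reported interval and a comparison that retains relapsers' final scores. CGI-TS Improvement also loses its treatment difference, but no baseline adjustment was ever planned for it.

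**What to change.** In SAP 8.2.1, state that the double-blind summaries are by treatment group. At the last-visit row of CT-5.2.2, CT-5.3.2 and CT-5.4.2, add each aripiprazole arm's difference from placebo with a 95% CI, from an ANCOVA with treatment and randomization-baseline score. Use last visit as defined in SAP 5.2, and say that it includes relapse exits, completers and administratively truncated subjects. Label the result as exploratory estimation without formal testing.

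In SAP Section 14, name the MMRM, the LOCF ANCOVA as originally specified, and the missing-not-at-random sensitivity analyses as not performed, with the reason.

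The cost is some SAP wording and one simple model per endpoint. The downsides are wide intervals if few subjects were randomized and an outcome that behaves like last observation carried forward.
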